1.1 Background of Clinical Study

World Kidney Day (WKD) is celebrated every Thursday on the second week in March. In 2017, the theme raised was "Kidney disease and obesity, a healthy lifestyle for healthy kidneys", which Chronic Kidney Disease (CKD) is a global public health problem with increased prevalence and incidence of kidney failure, poor prognosis, and high cost. Clinically, CKD is defined as kidney damage and / or decreased Glomerular Filtration Rate (GFR) of less than 60 ml / minute / 1.73 m² for a minimum of 3 months (KDIGO, 2012).

CKD is also a comorbidity of diabetes and hypertension, and can also be caused by chronic glomerulonephritis, chronic interstitial nephritis, polycystic kidney disease, urinary tract infections, and obesity. CKD also has an indirect impact on increasing deaths from cardiovascular disease, diabetes, hypertension, infections in people with HIV, and malaria (Indonesia Ministry of Health, 2017).

Based on 2015 data by the Global Burden of Disease, 1.2 million deaths are directly correlated with a decrease in glomerular filtration ability. In addition, it is also estimated that 2.3-7.1 million deaths due to difficulty accessing dialysis, 1.7 million deaths from acute kidney failure, and 5-10 million deaths from other kidney diseases (Luyckx et al., 2018).

In Indonesia, treatment of CKD patients is second rank after heart disease in the largest funding of BPJS health. Based on the results of the 2013 Basic Health Research (Riskesdas), 0.2% of the adult population were diagnosed with CKD. This number is lower than the prevalence of CKD in other countries based on Indonesia Renal Registry (Pernefri) 2006, which is 12.5%. The difference in prevalence rates caused by the diagnosis of CKD patients in Indonesia can only be done in the later and final stages (Indonesia Ministry of Health, 2013).

The prevalence of CKD increases as the increasing number of elderly people and the incidence of diabetes mellitus and hypertension. CKD is also more common in women because women generally have lower muscle mass, so the serum creatinine concentration is also different. Calculation of prevalence of CKD generally involves correction factors for women with CKD (Hill et al., 2016).

Anemia, which is a complication of chronic kidney disease, is often associated with decreased levels of erythropoietin (EPO) in the blood. This results from damage of the cell mass in the kidneys responsible for EPO production. Treatment of anemia caused by chronic kidney disease which has become the standard is the administration of exogenous EPO together with improvement in blood iron levels.

EPO is a glycoprotein hormone produced by renal erythropoietin-producing cells and has a function in inducing red blood cell production in the red marrow. Today, EPO has been developed on a manufacturing scale using recombinant technology to meet market needs. EPO which is developed using recombinant technology is called recombinant human EPO (rhEPO). The first recombinant human EPO was developed by Epoetin alpha by Amgen Inc. with the name Epogen market. Some other rhEPO products that have been widely used throughout the world include Procrit® from Amgen Inc. and Eprex® from Janssen Pharmaceutica (Zadeh, 2017).

In Indonesia, several RhEPO products that have obtained marketing licenses include Epodion®, Epoglobin®, Epotrex®, Hemapo®, Rinofer®, and Recormon® (MIMS, 2019; BPOM, 2019). These products are developed by both Indonesian and international pharmaceutical companies. The rhEPO products are categorized as biosimilar products. RhEPO products in Indonesia were developed referring to the RhEPO originator so that they have the same efficacy and safety as the rhEPO originator.

Similar biotherapeutic product (SBP) or can be called similar biological products are biological products with efficacy profiles, safety, and quality that are similar to biological products approved by the drug safety regulatory authority (BPOM, 2015). Development of biological products that are not as simple as synthetic chemical drugs can cause several aspects of similar product development to be different. The development of generic drugs from synthetic chemical drugs can go through the same stages and produce types of drugs with the same characteristics as the originator. However, this does not apply to the development of biological products.

Biological products are complex molecules that are produced using living cells and have very high levels of variation depending on the means, tools and materials used in the production process. The consistency between batches of production is a challenge in manufacturing biological products. Insignificant differences or very small changes in production, transportation or storage can result in changes in the safety and efficacy profile of biological products. Two similar biological products cannot always be proven to be identical products.

Biosimilar products can be produced by the pharmaceutical industry after the originator's product patent period has expired. At present, various biosimilar products are under development or have received marketing licenses in many countries. Development of science as well as the growth of pharmaceutical industry in Indonesia has an impact on improving domestic biosimilar products. Various biosimilar products that have been developed in Indonesia include erythropoietin, monoclonal antibodies, and several growth factor products.

Epodion® research has been carried out in several countries including Korea and Thailand with good results. Phase III studies in Korea evaluated the safety and efficacy of Eposis® in 198 CKD patients (Eposis®: 101, reference product: 97) using dose: ≤ 2000 IU / kg, 3 times/week. The efficacy of Eposis® is the same and or better than the reference product. Eposis also shows lower frequency of Adverse Events compared to reference products. Whereas in the Post Marketing Surveillance study in Korea with the number of subjects 640 CKD patients for 4 years. In the results of the safety assessment, 55 and 13 cases of adverse event occurred in the general PMS study and the long-term PMS study, respectively (An incidence of adverse events was 9.02% and 18.57%, respectively; in the exact 95% confidence level). All the reported adverse events were considered that there was no causal relationship with product and therefore there were no adverse drug reactions.

Phase IV study begins after drug approval. Therapeutic use studies go beyond the prior demonstration of the drug's safety, efficacy and dose definition. Studies in Phase IV are all studies (other than routine surveillance) performed after drug approval and related to the approved indication. They are studies that were not considered necessary for approval but are often important for optimizing the drug's use. They may be of any type but should have valid scientific objectives.

1.2 Rationale for Clinical Study

1.2.1 Non-clinical Study

Nonclinical study was conducted based on “Guideline on non-clinical and clinical development of similar biological medicinal products containing recombinant erythropoietin” released by European Medicines Agency (EMA/jansse/CHMP/BMWP/301636/2008). In pharmacology studies, biosimilarity and bioequivalence of test product and reference product was confirmed in the regular animal model, acute blood loss induction model, and renal failure model. Both articles’s effects were determined to be equivalent. In pharmacokinetic studies, all parameters, blood concentration curve area (AUC_{last}), maximum blood concentration (C_{max}), and half-life (T_{1/2}), met the criteria for biosimilarity evaluation.

Biosimilarity and bioequivalence of reference and test product on the absorption was confirmed in intravenous and subcutaneous administration in rats. In the case of toxicology study, no abnormality was observed in the single dose toxicity studies in rats and beagle dogs. To investigate the toxicity caused by the 4-week repeated intravenous administration of test product, it was repeatedly administered intravenously to Sprague-Dawley rats for 4 weeks.

As a result of the test, there was no death rate or any abnormality in the ophthalmologic test, urinalysis, autopsy, and clinical signs caused by the administration of test product. When compared to reference product, test product showed that equivalent or non-inferior toxicological profile. For analysis of antigenicity, active systemic anaphylaxis test (ASA) and passive cutaneous anaphylaxis (PCA) were conducted in guinea pigs. Both articles had similar pattern in anaphylaxis reaction.

From the pharmacodynamics, pharmacokinetic and toxicology study results of test product and comparison with reference product, test product was proven that has similar pharmacokinetics, pharmacodynamic effect and toxicological profile with reference. In conclusion, no harmful effect is expected to be observed when test product is administered into human.

1.2.2 Clinical Safety Study

Post-marketing data was collected from December 4, 2007 to December 3, 2011 in Korea. A target number of subjects were more than 600 and the total number of collected CRFs was 640. Detailed report was attached in 5.3.6 Report of post-marketing experiences. In the results of safety assessment, 55 and 13 cases of adverse event occurred in the general PMS study and the long-term PMS study, respectively (An incidence of adverse events was 9.02% and 18.57%, respectively; in the exact 95% confidence level). All the reported adverse events were considered that there was no causal relationship with product and therefore there were no adverse drug reactions.

1.2.2 Efficacy Study

Therapeutic confirmatory study for evaluating the safety and efficacy of EPO PRODUCT on CRF (Chronic Renal Failure) patients: a double-blinded, randomized, active drug-comparative, parallel-designed, multi-center clinical study has been conducted on 192 patients in Korea. To verify the effects of treating anemia patients suffering from chronic renal failure, the indications of the test product and the reference product and trends in changes in RBC (Red Blood Cell), Hemoglobin, Hematocrit, and Reticulocyte, were examined during the period of clinical study.

During the process of the clinical study, the test group posted somewhat higher values compared with the reference group in 3 items, i.e., RBC, Hemoglobin, and Hematocrit.

1.3 Objective and Hypothesis

The objective of this study is to evaluate the safety and efficacy of Epodion® on Chronic Kidney Disease (CKD) patients.

1.3.1 Study Objectives

1.3.1.1 Efficacy Outcome

A. Primary Objectives

To demonstrate that the Epodion® treatment is equivalence to Eprex® by evaluating Hb level change between baseline and evaluation period.

B. Secondary Objectives

1. Obtain data mean change in weekly dosage per kg body weight between the baseline period and the evaluation period.
2. Calculating instability rate of Hb (hemoglobin) level during maintenance and evaluation period as defined when Hb (hemoglobin) level dropped below 8 g/dL or increase more than 13 g/dL.
3. Evaluating Hb (hemoglobin) and Hematocrit level during maintenance and evaluation period.

1.3.1.1 Safety Outcome

Obtain safety data (side effects, adverse events, and serious adverse events) hemodialysis patients during the use of Epodion®.

1.3.2 Hypothesis

Efficacy and safety of Epodion® was therapeutically equivalence to the reference product (Eprex®) in dialysis patients with renal anemia.

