Randomization ³⁾																										
Concomitant Medication																										
Eprex® administration ²⁾									Administer at an appropriate level for each subject																	
Epodion® administration ²⁾									Administer according to the existing baseline dosage																	
Lab Test	CBC (Hb)	■	■	■	■	■	■	■	■	■	■	■	■	■	■	■	■	■	■	■	■	■	■	■	■	
	CBC (Hct)	■							■	■	■	■	■	■	■	■	■	■	■	■	■	■	■	■	■	
	Iron status	■							■	■	■	■	■	■	■	■	■	■	■	■	■	■	■	■	■	
	HIV	■																								
Blood Chemistry (ALT&AST)		■																								
		■																								
Pregnancy Test	■																									
Safety Assessment ⁴⁾									Every time																	

1. Subject must achieve baseline target Hb level 10-12 g/dL prior enter maintenance period. If during 4-week titration period subject did not achieve baseline Hb level 10-12 g/dL, titration period will be extended maximum until week 8.
2. Doses must be individualized to ensure that hemoglobin is maintained at an appropriate level for each subject. In the screening period, initial dose is 50 IU/Kg body weight three times per week. During titration, dose id titrated closely to achieve baseline Hb level 10-12g/dL. In maintenance period administer Eprex® and Epodion® equal previous stable dose in titration period. Dose is allowed to be increased or decreased during maintenance period at an appropriate level according to the condition of the subjects.
3. Only the subjects within the inclusion/exclusion criteria and achieved baselinetarget evaluation criteria should be processed to randomization and maintenance period. When the subject achieves baseline target Hb level 10- 12 g/dL in 4 weeks titration period randomization will be done in week 8, if subject fail achieves Hb 10-12 g/dL in 4 weeks titration period, titration period will be extended until week 8. Subject will be screened failure and cannot enter maintenance period if during maximum 8 week titration cannot achievetarget baseline Hb level 10-12 g/dL.
4. Safety assessment will be evaluated based on comparison incidence of adverse event between Epodion® and Eprex®. Incidence of adverse eventswill be recorded during maintenance and evaluation period.

CHAPTER I. INTRODUCTION

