7.2 General principle of statistics

The summary statistics will be presented with descriptive statistics including number of subjects, mean, standard deviation, median, minimum and maximum values for continuous variables. For categorical variables, number and percentage of subjects with event will be presented. For the test of significance between the two treatment groups, the two-sided test will be conducted at 5% significance level.

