7.4.1 Primary Endpoint

Change in Hb levels from baseline to the evaluation period

Descriptive statistics will be provided by treatment group. The difference between treatment groups will be determined by ANCOVA (analysis of covariance) model with treatment as factor, and baseline Hb level and the change in weekly dosage per kg body weight from baseline to the evaluation period of Epodion® or Eprex® as covariates.

Therapeutic equivalence of Epodion® to the comparator Eprex® will be demonstrated if the two-sided 90% confidence interval of the difference of mean changes in Hb levels between treatment groups lay within the interval of ± 0.5 g/dL.

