7.4.2 Secondary Endpoint

(1) Change in weekly dosage per kg body weight from baseline to the evaluation period.

Descriptive statistics will be provided treatment group. The difference between treatment groups will be analyzed by ANCOVA model with treatment as factor, and baseline Hb level and baseline weekly dosage per kg body weight value as covariates.

(2) Instability rate of Hb level during maintenance and evaluation period

The number of subjects with Hb level <8 g/dl or Hb level >13 g/dl during maintenance and evaluation period will be provided by treatment groups along with rates and the two-sided 95% confidence intervals. Also, the difference in the rates between the treatment groups and two-sided 95% confidence interval will be provided.

(3) Hb and Hematocrit level during maintenance and evaluation period

Descriptive statistics will be provided treatment groups for Hb and Hematocrit levels at baseline and at each bi-week during maintenance and evaluation period. The time course figure of Hb levels will be presented using mean and standard deviation throughout maintenance and evaluation period.

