7.5 Safety Analysis

Safety analysis will be performed using the Safety Set.

(1) Adverse events (AEs)

The incidence of the following events will be summarized by treatment group for all observed adverse events, local reactions and systemic reactions.

- Treatment-emergent adverse events (TEAEs)
- Adverse Drug Reactions (ADRs)
- Serious TEAEs/ADRs
- TEAEs/ADRs leading to investigational product discontinuation
- TEAEs/ADRs leading to death

(2) Vital sign, Laboratory test

Summary statistics for change from baseline in vital signs and the laboratory test evaluation will be provided. Clinically significant abnormal results in laboratory test will

also be summarized. If needed, laboratory re-tests may be carried out outside the schedule to monitor the patient's condition.

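### The hypothesis in Protocol 1.3.2 claims equivalence for safety as well as efficacy, but the objectives, decision rule and sample size cover haemoglobin only, and the announced adverse-event comparison has no stated method

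*Protocol*

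**What the plan says.** Protocol 1.3.2 (Hypothesis) reads: "Efficacy and safety of Epodion® was therapeutically equivalence to the reference product (Eprex®) in dialysis patients with renal anemia". This is the only formal hypothesis in the documents.

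Other sections treat safety differently:

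- **Objectives.** The primary objective (Protocol 1.3.1.1, Efficacy Outcome) ties equivalence to the Hb change alone. The safety objective (1.3.1.1, Safety Outcome) is descriptive and names only the test product: "Obtain safety data (side effects, adverse events, and serious adverse events) hemodialysis patients during the use of Epodion".
- **Announced comparison.** Footnote 4 to the study timeline in the synopsis says: "Safety assessment will be evaluated based on comparison incidence of adverse event between Epodion® and Eprex".
- **Decision rule.** Protocol 7.4.1 begins: "Therapeutic equivalence of Epodion® to the comparator Eprex® will be demonstrated if the two-sided 90% confidence interval". It goes on to require that the interval for the difference in mean Hb change lie within ±0.5 g/dL. SAP 3.1 gives the same rule.
- **Sample size.** Protocol 3.2 (Rationale Number of Subject) uses Hb inputs only: difference 0, SD 0.8 g/dL, margin ±0.5 g/dL.
- **Safety analysis.** Protocol 7.5 and SAP 3.3.1 say: "The incidence of the following events will be summarized by treatment group for all observed adverse events, local reactions and systemic reactions". They give no difference, interval, margin or test.
- **General test rule.** Protocol 7.2 and SAP 2 say: "For the test of significance between the two treatment groups, the two-sided test will be conducted at 5% significance level". This rule is not assigned to any safety variable.

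**The concern.** The hypothesis puts efficacy and safety into one equivalence statement, and only the efficacy half has a margin and a rule. The rule in 7.4.1 uses the same term as 1.3.2, therapeutic equivalence, without limiting it to efficacy. A report author could meet the Hb rule, cite 1.3.2, and present equivalent safety as shown.

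Safety is also described in three ways that do not agree: data to be collected (1.3.1.1), incidence to be compared between arms (synopsis footnote), and equivalence (1.3.2). The analysis sections supply only by-arm summaries, so they provide neither an estimate for the comparison nor a basis for equivalence. What is at stake is the wording of the safety conclusion. In arms of 50, similar-looking AE percentages are compatible with sizeable true differences.

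**Working it through.** **Plan's own figure.** The documents give no sample size, power or margin for safety, so there is no safety figure to reproduce. The one sample-size figure, 90 in total at 90% power, is for Hb. The stated inputs do not return it: exact t-based power for two one-sided tests (TOST) is 80.5% at 90 in total, and 114 in total are needed for 90%. The SAS output is not shown, so the cause cannot be seen. That is a separate matter. What counts here is that no input to the calculation is an AE rate.

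**Inputs.** 50 per arm (Protocol 3.2.1). The Safety Set counts everyone dosed, so 50 is not reduced for dropout. The only AE rates in the documents are 9.02% and 18.57%, from Korean post-marketing studies (Protocol 1.1 and 1.2.2). They serve as illustrations, not as forecasts for this trial. Rates of 20%, 30% and 40%, and all safety margins below, are assumptions.

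**Step 1: precision of an AE-rate difference.** With equal true rates p, the 95% half-width is 1.96 × √(2p(1−p)/50).

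| p | Source | 95% half-width (percentage points) |
|---|---|---|
| 9.02% | documents | 1.96 × √(2 × 0.0902 × 0.9098/50) = 11.2 |
| 18.57% | documents | 1.96 × √(2 × 0.1857 × 0.8143/50) = 15.2 |
| 20% | assumed | 15.7 |
| 30% | assumed | 18.0 |
| 40% | assumed | 19.2 |

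At 9.02% the half-width exceeds the rate itself.

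**Step 2: rare events.** With 0 events in 50, the one-sided 95% upper bound is 1 − 0.05^(1/50) = 5.8%. The chance that an arm of 50 shows at least one case of a 1% event is 1 − 0.99^50 = 39.5%.

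**Step 3: power for safety equivalence, had it been tested.** The assumed rule is a 90% interval for the rate difference lying inside the margin, with equal true rates. Power at 50 per arm comes from full binomial enumeration with the Newcombe interval.

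| Margin (points) | p = 9.02% | p = 18.57% | p = 30% (assumed) |
|---|---|---|---|
| ±5 | 0% | 0% | 0% |
| ±10 | 9.1% | 0.1% | 0% |
| ±15 | 59.7% | 24.2% | 5.5% |
| ±20 | 89.8% | 65.0% | 44.3% |

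The number per arm for 90% power, by the normal approximation 2p(1−p)(1.645 + 1.645)²/margin², is 711, 178, 79 and 45 for margins of 5, 10, 15 and 20 points at 9.02%. At 18.57% it is 1310, 328, 146 and 82. The approximation is slightly more favourable than the enumeration at ±20 points and 9.02%.

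**Step 4: could the general 5% test fill the gap?** It tests for a difference, and a non-significant result would not show equivalence. At 50 per arm it has 80% power only for contrasts of about 9% versus 32%, or 19% versus 45%.

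**The case against.** The strongest reply is that the operative text already separates the two. The primary objective and the decision rule name Hb, the safety objective is descriptive, and the SAP contains no safety hypothesis. On that view 1.3.2 is one loosely worded sentence, and by-arm AE tables are adequate for an objective to collect safety data. Much of this stands. It keeps the point minor, and it shows that the proposed wording brings 1.3.2 into line with the rest of the plan. It does not remove the conflict: 1.3.2 still asserts safety equivalence, and the synopsis footnote still promises a comparison that by-arm tables leave without an estimate.

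Three stronger readings are tempting, and the documents do not support them.

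- A reader might infer that meeting the Hb rule formally confirms 1.3.2, safety included. No section says the hypothesis is accepted or rejected as a unit. The shared term makes that misreading possible, not certain.
- A reader might say there is no test at all. Protocol 7.2 and SAP 2 contain a general two-sided 5% test. The accurate statement is that no equivalence test is specified for safety and no test is assigned to it.
- A reader might say 50 per arm can never support safety equivalence. That depends on a margin the documents never set. With ±20 points at a 9.02% rate, power is about 90%, though that margin is more than twice the rate.

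**Conclusion.** The point holds as an inconsistency with a modest practical consequence. Protocol 1.3.2 claims equivalence for safety, while the objectives, the rule and the sample size support an equivalence conclusion on Hb change only. The announced AE comparison has no stated estimate or interval.

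The size depends on the AE rate. The 95% half-width is about 11 and 15 points at the two rates in the documents, and about 16 to 19 points at assumed rates of 20% to 40%. Under assumed margins of ±10 points or less, power for safety equivalence is below 10% at every rate shown. At ±15 points it is at most about 60%. These figures assume 50 per arm and equal true rates. The primary Hb estimate and its decision rule are not affected.

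**What to change.** - **Protocol 1.3.2:** restrict the equivalence hypothesis to the change in Hb, and describe safety as a descriptive between-arm comparison.
- **Protocol 7.5 and SAP 3.3.1:** add the between-arm risk difference with a two-sided 95% confidence interval for treatment-emergent AEs, serious treatment-emergent AEs, and treatment-emergent AEs leading to discontinuation. The plan already does this for Hb instability in Protocol 7.4.2 and SAP 3.2: "Also, the difference in the rates between the treatment groups and two-sided 95% confidence interval will be provided". It would also supply the comparison promised in the synopsis footnote.
- **Same sections:** state that no conclusion of safety equivalence will be drawn.

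If the sponsor wants a safety-equivalence claim, it would have to define a safety endpoint and margin and size the trial for them. Step 3 shows what that implies.

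The cost is protocol and SAP wording and a small amount of extra table output, with no added subjects, visits or data. The downside is a narrower claim.
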